TBI	Traumatic Brain Injury
TMF	Tral Master File
TMG	Trial Management Group
TSC	Trial Steering Committee
VTE	Venous Thromboembolism

5. Trial Flow Chart

Primary outcome measure:

- Clinically relevant VTE within 30 days from randomisation, to include any confirmed diagnosis of symptomatic DVT, pulmonary embolism or death related to VTE

Secondary outcome measures:

- Proximal DVT at asymptomatic screening ultrasound (only relevant for sites where they undertake screening ultrasound as part of routine clinical practice)
- Progression of intracranial haemorrhage within 14 days after randomisation requiring neurosurgical intervention
- Progression of intracranial haemorrhage on routinely performed Imaging
- Adverse events including major and clinically relevant non major bleeding events (assessed and reported in accordance with criteria published by the International Society of Thrombosis and Haemostasis)
- VTE at 90 days
- 7-day, 30-day, and 12-month mortality
- Glasgow Outcome Scale-Extended (GOS-E) at 6 and 12 months
- Quality of life (EQ5D-5L) at Day 30 or discharge, 6 and 12 months
- Length of stay of index admission
- Economic analysis

6.1 Background

Every year in the UK, an estimated 1.4 million people suffer a Traumatic Brain Injury (TBI) and 200,000 people with TBI are admitted to hospital (1). Following a TBI, patients are at considerable risk of morbidity and mortality for several reasons, including the development of venous thromboembolism (VTE) (2). The most common types of VTE are deep vein thrombosis (DVT) and pulmonary embolism (PE). These problems can complicate recovery from TBI, lead to a longer-term reduction in quality of life and can occasionally be fatal.

Recent systematic reviews have reported a VTE incidence rate following TBI of approximately 10% (3–5). The aetiology of provoked VTE in TBI patients is multifactorial, including prolonged immobility, motor deficits, presence of extracranial injuries, inflammatory cascades, and hyper-coagulability (5–7). The prothrombotic state following traumatic injury has been attributed to many factors, including decreased levels of functional protein C and abnormal antithrombin levels (8).

VTE events are of great clinical concern. TBI patients already face complex recovery from their initial injury, and additional complications, including VTE, have been shown to worsen their outcomes by lengthening hospital stays and reducing their likelihood of being discharged home (9). Therefore, developing effective strategies to prevent VTE in patients with TBI is essential and a priority in this patient group.

In hospitalised patients, national guidelines recommend using mechanical VTE prophylaxis and early initiation of pharmacological VTE prophylaxis (PTP) for appropriate patient populations (10). In a broad population, this has reduced VTE-related deaths up to 90 days after discharge by 15.4% in the last 12 years (11). However, there are no clear national guidelines on VTE prophylaxis following TBI, including PTP; risk assessment models have not been validated in these patients (12,13). This lack of evidence is also reflected in the Brain Trauma Foundation guidelines (4th edition), stating there is insufficient Level I or II evidence to make recommendations on the timing of PTP in TBI (13). Recent work in patients without TBI suggests a lower bar for prescribing thromboprophylaxis could improve outcomes and make the best use of NHS resources (9,14).

Low-molecular-weight heparin (LMWH) agents are the first choice for PTP due to their favourable safety profile and ease of administration (15). Several studies have evaluated the rate of VTE and TBI progression following early implementation of LMWH PTP. They have been summarised in 7 systematic reviews (3,4,16–20). Three reviews performed a pooled meta-analysis of rates of VTE between patients treated with early or late pharmacological VTE prophylaxis. The 2013 and 2016 meta-analyses included the same 5 studies with a 72-hour cut-off between early and late thromboprophylaxis. Of 1624 patients in total, the pooled risk ratio for VTE was 0.52 (95% CI 0.37–0.73) in favour of early PTP (3,19). The 2018 meta-analysis included 11 studies grouped into 3 early subgroups (<24, <48, or <72h) of PTP, with a pooled odds ratio across all time groups of 0.58 (95% CI 0.38–0.87), again favouring early PTP (16). The meta-analyses did not include a randomised double-blinded placebo-controlled pilot trial conducted in 2012, recruiting 62 patients to receive LMWH (n=34) or placebo (n=28) at <96h from TBI (21). One DVT was reported in the placebo arm, but no VTE in the LMWH arm. Additional systematic reviews without meta-analyses report reduced VTE with early PTP (4,17,18,20). TBI progression rate was assessed by pooling individual study results, with no statistically significant difference in rate found between early and late arms overall (3,19).

The literature demonstrates a reasonable safety profile with early PTP administration and supports the TOP-TBI protocol, v1.1, 15 January 2025

clinical effectiveness of early PTP. This evidence has limitations specific to observational methodology.

Current national guidance does not make any recommendations regarding PTP timing. The current risk assessment model recommended by NICE highlights any neurosurgical admission as a risk factor for bleeding and suggests that '*clinical staff should consider if bleeding risk is sufficient to preclude pharmacological intervention*'. NICE guidance states that PTP should be offered to people with serious or major trauma as soon as possible after the risk assessment when the risk of VTE outweighs the risk of bleeding but also that PTP should not be offered to patients with traumatic intracranial haemorrhage until the patient's condition has stabilised. These recommendations are entirely open to clinician interpretation and discretion, resulting in significant variation in practice even for patients with similar characteristics (10). Our service evaluation suggests these recommendations may dissuade clinicians from prescribing PTP.

6.2 Why is this research required?

VTE during hospitalisation is the leading cause of disability-adjusted life-years (DALYs) lost in low-income and middle-income countries and the second most common cause in high-income countries (22, 23). VTE incidence rises with increasing age, placing the rising number of elderly TBI patients at significant risk (23). TBI patients are at considerable risk of developing complications if VTE occurs, as standard treatment options (therapeutic anticoagulation) may complicate recovery and adversely affect long-term functional outcomes, prolonging hospitalisation and increasing inpatient costs (24). PEs are a leading cause of delayed mortality in TBI patients, lengthening hospital stays and reducing the likelihood of being discharged home (25–27). A considerable body of evidence suggests that administration of PTP can reduce the incidence of VTE in patients with TBI (22, 24). This, in turn, can reduce mortality and morbidity and improve long-term functional outcomes and quality of life of patients with TBI. However, there is often a reluctance to initiate PTP early due to the lack of high-quality evidence demonstrating superior clinical effectiveness. This results in heterogeneous management of VTE risk in TBI patients with PTP use being dependent on the individual clinician, hospital, or service practice. There is a need to generate high-quality new knowledge, which this trial has the capacity to do. The results of a high-quality study will be used to inform practice guidelines in the NHS and beyond. The simplicity of the intervention being studied, the wide availability of LMWH, and our comprehensive dissemination plan mean that the TOP-TBI outputs can be rapidly incorporated into patient care and pathways.

The study is supported by the Society of British Neurological Surgeons (SBNS), Neuro Anaesthesia & Critical Care Society (NACCS), and Intensive Care Society (ICS).

6.3 Preliminary work

We have undertaken a retrospective cohort study and a UK-wide survey gathering data on the timing of PTP in patients following TBI. Our retrospective study included 731 patients over a six-month period and had participation from five neurosurgical centres. This study showed that 1) there was much heterogeneity in the timing of initiating PTP among different centres, 2) patients with major extracranial injuries were more likely to receive PTP and 3) PTP did not appear to exacerbate haemorrhagic intracranial lesions. Our UK-wide survey included responses from 61 individuals from 26 neuroscience units. The results showed 1) 85% of respondents agreed there is no high-quality evidence on the timing of starting PTP after an acute TBI and 2) the most common factors contributing to decision-making before starting VTE prophylaxis included progression of intracranial haemorrhage, new intracranial haemorrhage and prevention of VTE events. Thus, our preliminary work provides further evidence for the pressing need for standardised guidelines on this subject.

6.4 PTP Agents and Mechanism of Action

Our preliminary work has shown that LMWH are the most used drugs for pharmacological thromboprophylaxis in the UK in patients with TBI. However, there may be instances where another drug (that is not a LMWH) may be used for PTP.

For example, Muslim religious leaders have previously issued guidance that use of porcine derived LMWHs are suitable for use in life-threatening conditions, but their use should be discussed with individual patients, if this is possible. Alternatively, Fondaparinux, as a synthetic anticoagulant, may be a suitable alternative for patients who wish not to receive porcine material.

We plan to allow use of local trust protocols for anticoagulants for PTP with respect to the agent used, weight adjustment and renal dosing regimens, and will extend this to use of alternative agents for those patients/families who wish to participate in the trial but pursue non porcine options.

This will ensure the trial remains pragmatic and inclusive to patients from all populations.

We provide an overview and the mechanism of action of the most used PTP (LMWH) below.

Overview

Low molecular weight heparins (LMWHs) are a family of drugs named “Parenteral anticoagulants”. LMWHs include the following drugs: dalteparin sodium, enoxaparin sodium and tinzaparin sodium. The National Institute for Health and Care Excellence (NICE) and the British National Formulary (BNF) have stated that LMWHs have approval for the following:

- DVT prophylaxis in medium and high-risk patient groups (surgical, orthopaedic and medical patients)
- Treatment of VTE in pregnancy
- Treatment of VTE in non-pregnant women
- Treatment of STEMI
- Unstable angina
- Prevention of clotting in extracorporeal circuits

Mechanism of action

Low molecular weight heparins are anticoagulant drugs acting by inhibition of the final common pathway of the coagulation cascade. The overall aim of the coagulation cascade is to fluid blood into a clot and thus prevent bleeding. The final aspect of the common pathway is to convert fibrinogen into fibrin by the activity of thrombin. LMWH inhibits coagulation by activating antithrombin III. Antithrombin III binds to and inhibits factor Xa. By inhibiting factor Xa, antithrombin III prevents the activation of the final common pathway. Factor Xa inactivation means prothrombin is not activated to thrombin, and thus fibrinogen is not converted to fibrin for the formation of a clot. LMWH is a small fragment of a larger mucopolysaccharide, heparin. Heparin works similarly by binding antithrombin III and activating it. Heparin also has a binding site for thrombin so that thrombin can interact with antithrombin III and heparin, thus inhibiting coagulation. Heparin has a faster onset of anticoagulant action as it will inhibit Xa and thrombin, while LMWH acts only on Xa inhibition (28).

LMWH is obtained by fractionation of polymeric heparin. It differs from unfractionated heparin in several ways, including the average molecular weight; the need for only once or twice daily dosing; the absence of monitoring the activated partial thromboplastin time (aPTT); and the lower risk of bleeding, osteoporosis, and heparin-induced thrombocytopenia (HIT). In addition, the anticoagulant effect of

heparin is reversible with protamine sulphate, whereas its effect on LMWH is limited (29).

There are many agents that are licensed to provide VTE prophylaxis. The agent used differs depending on the Trust policy. However, they all prevent thrombus formation or extension of an existing thrombus in the venous side of the circulation. A thrombus consists of a fibrin web enmeshed with platelets and red cells.

Table 1: The table below gives an overview of the different agents available for VTE prophylaxis. NICE guidelines provide further details on their use and administration.

Heparin	
• Short duration of action• Often referred to as “standard” or heparin (unfractionated) to distinguish it from low molecular heparins• Used in patients at high risk of bleeding since its effects can be terminated quickly by stopping the infusion
Low molecular weight heparins (LMWH)	
• Drugs under this class include: dalteparin sodium, enoxaparin sodium and tinzaparin sodium• Preferred over heparin (unfractionated) in the prevention of VTE since they are as effective and have a lower risk of heparin induced thrombocytopenia• The prophylactic regime does not require anticoagulant monitoring• Duration of action is longer than heparin (unfractionated) thus once daily subcutaneous administration possible
Heparinoids	
• Drugs under this class include: danaparoid sodium• Used primarily for prophylaxis of DVT in patients undergoing general or orthopaedic surgery and patients who develop heparin induced thrombocytopenia
Fondaparinux sodium	
• Used for VTE prophylaxis in patients undergoing major orthopaedic surgery of the hip or leg or abdominal surgery or medical patients who are immobilised because of acute illness
Oral anticoagulants	
• Drugs under this class include: Apixaban, Rivaroxaban, Dabigatran, Edoxaban and Warfarin• Apixaban, Rivaroxaban, Dabigatran, Edoxaban are licenced for the prevention of recurrent DVT and PE in adults• Warfarin is licenced for prophylaxis for DVT and PE

Traumatic brain injury patients are likely to have many other pathologies; thus, a clinical decision may be made to use a specific drug for PTP that may not be licenced. To ensure the trial remains pragmatic, the drug used for PTP can be based on hospital guidelines/clinician discretion, even if its use is deemed unlicensed. However, from our survey of 26 neuroscience centres in the UK, the most used LMWH for VTE prophylaxis in patients with TBI.

Patients enrolled on this trial can only be prescribed agents listed in this table.

7. Rationale of the trial

The overall aim of the TOP-TBI trial is to define best practices in the timing of venous thromboembolism prophylaxis in adult patients following a traumatic brain injury. We describe the trial below in the PICO format and in more detail thereafter.

Population	Adult (≥ 16 of age) patients who have sustained an acute traumatic brain injury and require admission to a hospital
Intervention	Early pharmacological thromboprophylaxis (PTP) administration (<72 hours from injury)
Control	Late PTP administration (prescription of PTP deferred by a minimum of 120 hours from injury or PTP not prescribed at clinical discretion)
Outcome	Clinically relevant Venous thromboembolism (VTE) within 30 days from randomisation

8. Trial design

8.1 Statement of design

TOP-TBI is a multi-centre, parallel-group, pragmatic, randomised superiority trial to determine the clinical- and cost-effectiveness of early PTP administration versus late administration for adult patients with TBI.

The study will be preceded by an internal pilot to confirm recruitment, randomisation, treatment, and follow-up assessments. We have defined robust progression criteria (section 8.3) based on recently published recommendations (30). On reaching the pre-defined success criteria, the internal pilot studies will run seamlessly into the main trial.

8.2 Number of centres

Patients will be recruited primarily from adult neuroscience units (NSU) in the NHS. We anticipate that we will include the majority of Major Trauma Centres (MTC), approximately 20 UK sites, as these are the hospitals where most of the target patient population are directly transferred after a serious TBI.

The pilot stage will last 6 months, and we will recruit 150 patients. After successfully completing the pilot stage, the substantive trial stage will follow and will encompass, where possible, all remaining neuroscience centres and selected major acute NHS hospitals in the UK. If feasible, we will also aim to expand the trial to our overseas partners who have participated in our previous trials over the last 10 years.

Initiation of sites will be undertaken according to CCTU internal processes. Conditions and documentation required for site activation will be detailed on the trial-specific Participating Initiation Checklist maintained in the TMF and must be fully completed prior to opening sites to recruitment.

8.2.1 Principal Investigator Responsibilities

The PI's responsibilities will be listed in the Participating Site Agreement; they will be expected to retain oversight of the trial conduct and documentation at the site, attend the site initiation visit (SIV), maintain the ISF, ensure staff receive the appropriate training and that they are fully aware of their delegated responsibilities, record and report safety events within expected timelines, and update the lead site coordination team if there have been changes at the site that would impact on the sites ability to contribute to the clinical trial.

8.3 Number of participants

We will recruit 1512 patients in total (150 in the internal pilot and 1362 in the substantive study). The pilot phase will last approximately 6 months. Progression criteria based on recruitment for the pilot phase to run into the substantive phase are described in the table below.

	Red	Amber	Green
% of rate proposed	<50% (≤ 74)	50-99% (74-149)	100% (150)
Number of sites opened	<7	7-12	13
Average number of patients/site/month	<1.0	1.0-1.98	2
	Discuss with oversight groups (TMG, TSC) consider feasibility of continuing to main trial; draw up a recovery or closedown plan to discuss with NIHR	Discuss with oversight groups (TMG and TSC) and propose a recovery plan to NIHR	Proceed to main trial

Further progression criteria to progress from the pilot phase to the substantive phase are as follows:

- If the loss to follow-up exceeds 10% without an identifiable and correctable reason, it would not be feasible to progress to the main phase without substantial changes in the study design
- No ethical or safety concerns raised by the Trial Steering Committee (TSC)

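### The pilot progression table puts 74 patients in both red and amber and leaves rates between 1.98 and 2 without a colour; its green rate matches the 150-patient target only at 75 site-months

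*Protocol*

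**What the plan says.** Protocol section 8.2 sets the pilot's size and length: "The pilot stage will last 6 months, and we will recruit 150 patients". Section 8.3 repeats the 150 and calls the length approximate: "The pilot phase will last approximately 6 months".

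Section 8.3 then grades the pilot on three rows, from red through amber to green:
- Recruitment against target: "of rate proposed <50% (≤ 74) 50-99% (74-149) 100% (150".
- Site opening: "Number of sites opened <7 7-12 13".
- Recruitment rate: "Average number of patients/site/month <1.0 1.0-1.98 2".

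Each colour has its own action. Red asks the oversight groups to weigh whether the main trial is feasible and to prepare a recovery or closure plan for the funder. Amber asks for a recovery plan. Green means going on to the main trial.

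The protocol gives no site-opening schedule. It does not say whether the average rate is taken over open site-months or over sites times six.

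**The concern.** Progression criteria are useful because they are fixed before the pilot data are seen. Section 8.1 says the pilot runs on into the main trial once the pre-defined criteria are met. Section 15.4 gives no other defined stopping criteria and refers back to this table.

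A count with two colours, or a rate with none, has to be settled by judgement after the result is known. The rate row raises a further question. Its cut-offs look like 50% and 99% of 2 (0.50 × 2 = 1.0; 0.99 × 2 = 1.98), and nothing in the protocol links that 2 to 150 patients, 13 sites and 6 months. Whether the green cells describe one target or several then depends on a quantity that the protocol leaves undefined.

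**Working it through.** **Inputs**, all from Protocol sections 8.2 and 8.3: target 150 patients; 13 sites for green; about 6 months; count bands ≤ 74, 74-149 and 150; rate bands < 1.0, 1.0-1.98 and 2. The green values are read as minimums.

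**1. Count row.** Share of target = count / 150.
- 74/150 = 49.3%, below 50%, so red by percentage. It is also printed as the first amber count.
- 75/150 = 50.0%, the first count that fits the amber percentage.
- 149/150 = 99.3%, which rounds to the printed 99%.

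Only the lower amber limit is wrong, by one patient.

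**2. Gap in the rate row.** A rate r with 1.98 < r < 2 is in no band, and whole patients can produce one. At 78 site-months, 155/78 = 1.987. At 75 site-months, 149/75 = 1.987.

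**3. Do the green cells agree?** Rate = patients / site-months. With every site open throughout, site-months = 13 × 6 = 78.
- Patients needed for a rate of 2: 78 × 2 = 156, six more than the target.
- Rate at exactly 150 patients: 150/78 = 1.92, inside the printed amber band.
- Red limit of 1.0: 78 × 1.0 = 78 patients. So 75 to 77 patients would be amber by count and red by rate (75/78 = 0.96; 77/78 = 0.99).

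**4. Break-even.** 150 patients gives a rate of 2 at 150/2 = 75 site-months, a mean of 75/6 = 12.5 open sites. At 75 site-months the red limit agrees too: 75 × 1.0 = 75 patients. The printed rate cut-offs therefore fit the count row, with amber starting at 75, at 75 site-months and at no other value.

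**5. Staggered opening.** The protocol gives no schedule, so this range is an assumption: 13 sites opening evenly over the first T months, giving 13 × (6 − T/2) site-months.

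| T (months) | Site-months | Rate at 150 patients | Patients at a rate of 2 |
|---|---|---|---|
| 0 | 78 | 1.92 | 156 |
| 1 | 71.5 | 2.10 | 143 |
| 2 | 65 | 2.31 | 130 |
| 3 | 58.5 | 2.56 | 117 |

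Break-even is at T = 2 × (6 − 75/13) = 0.46 month. For 13 sites and 6 months, 1.92 is the lowest rate that 150 patients can give.

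**6. Length of pilot.** The duration is approximate. With all 13 sites open throughout, 5.75 months gives 150/(13 × 5.75) = 2.01 and 6.5 months gives 150/(13 × 6.5) = 1.78.

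**The case against.** The strongest defence is that the rows measure different things: total accrual, site activation and performance per site. A pilot whose sites open late but recruit well should be green on rate and amber on count, because that shows where the shortfall lies. Different colours on different rows are not an arithmetic error in themselves. This stands.

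A reader might infer that a pilot hitting its target exactly cannot be green on every row. The protocol does not support that. The figure of 1.92 needs all 13 sites recruiting from the first day of a full 6 months. The table counts sites opened, not sites open throughout, and section 8.2 requires an initiation checklist to be completed before each site opens, which makes a simultaneous start unlikely. Under even opening over one month or more, 150 patients is green on rate.

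A reader might also infer that total recruitment ought to decide the colour. That is a preference; nothing in the protocol ranks the rows.

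Finally, the consequence is limited. Red and amber both begin with discussion in the oversight groups and both go to the funder. Nothing stops automatically, and section 15.4 leaves recommendations on discontinuation to the steering committee. This also stands and keeps the point small. It does not remove the overlap at 74 or the gap below 2, which are present on any reading.

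**Conclusion.** Two faults hold without any assumption: 74 patients is both red and amber although 49.3% is red by the table's own percentage, and rates between 1.98 and 2 have no colour.

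A third holds conditionally. If all 13 sites are open for the full 6 months, the green rate implies 156 patients instead of 150, and 150 patients is graded amber on rate at 1.92. At 75 open site-months or fewer, all three green cells can be met together. Because the protocol does not define the denominator of the rate, it does not show which case applies.

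The size is one patient at the red/amber boundary, a band 0.02 wide with no colour, and a conditional difference of six patients (4% of 150) at the green boundary. Only the pilot progression rule is touched. The total of 1512 and the primary analysis are unaffected.

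**What to change.** In the section 8.3 table:
- Print the amber count as 75-149.
- Print the amber rate as 1.0 to < 2, or to below whatever green cut-off is chosen, so that no value is left out.
- State that the rate is per open site-month.
- Derive the rate cut-offs from the planned site-months S, so that they agree with the 150-patient target: green from 150/S, red below 75/S. With S = 75 the printed 2 and 1.0 can stay. With S = 78 they become 1.92 and 0.96.

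The cost is one table edit and a sentence of definition, agreed with the steering committee and the funder, best done before the pilot is judged. It has no effect on participants, on the total sample size or on the analysis.
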